## CLINICAL TRIAL PROTOCOL SYNOPSIS

Product:	Olaparib (AZD2281)
Protocol Number:	MedOPP044
EudraCT Number:	2015-001156-30
Protocol Title:	A preoperative “window-opportunity”, multicenter, pharmacokinetic-pharmacodynamic study to evaluate the inhibitory effects of single agent AZD2281 (Olaparib), in patients with early-stage endometrial carcinoma.
Short title:	Preoperative OLaparib in ENdometrial carcinoma (POLEN)
Target disease:	Endometrial carcinoma (EC)
Subjects:	Patients diagnosed with endometrial carcinoma prior surgery
Number of patients:	36 patients
Selection criteria:	
Patients are eligible for inclusion into the study only if they meet ALL of the following criteria:
 
Inclusion criteria
 
 
1. Patients must have histologically confirmed type I primary endometrial carcinoma (EC). Diagnosis biopsy must contain 3-12 mg of tumor cellularity/stroma (Tumor: 5-20 mm) and this will be checked in the central laboratory for this trial. If tumour cellularity/stroma is inadequate, one re-biopsy with adequate tumour cellularity/stroma will be mandatory before study entry.
 
2. Age <math>\geq</math> 18 years.
 
3. WHO performance status <math>\leq</math> 2.
 
4. Adequate bone marrow function as shown by ANC <math>\geq</math> 1.5 <math>\times</math> 10<math>^9</math>/L, Platelets <math>\geq</math> 100 <math>\times</math> 10<math>^9</math>/L, Hb <math>></math> 10g/dL.
 
5. Adequate liver function as shown by:           
 
o serum bilirubin <math>\leq</math> 1.5 <math>\times</math> ULN
 
 
 

- o INR < 1.3 (or < 3 on anticoagulants)
- o ALT and AST ≤ 2.5x ULN

6. Adequate renal function: serum creatinine ≤ 1.5 x mg/dL.

7. Fasting serum cholesterol ≤300 mg/dL or ≤7.75 mmol/L and fasting triglycerides ≤ 2.5 x ULN.

*NOTE: In case one or both of these thresholds are exceeded, the patient can only be included after normalization values with appropriate lipid lowering medication.*

8. Signed informed consent, including consent to tissue collection and blood samples as specified by the protocol.

#### **Exclusion criteria**

Patients will be excluded from the study if they meet ANY of the following criteria:

1. Subjects who have received prior anticancer therapies for the current endometrial cancer (including chemotherapy, radiotherapy, antibody-based therapy, hormonotherapy or surgery).
2. Patients, who have had a major surgery or significant traumatic injury within 4 weeks of start of study drug, patients who have not recovered from the side effects of any major surgery (defined as requiring general anesthesia) or patients that may require major surgery during the course of the study.
3. Prior treatment with any investigational drug within the preceding 4 weeks.
4. Patients receiving chronic, systemic treatment with corticosteroids or another immunosuppressive agent, except corticosteroids with a daily dosage equivalent to prednisone ≤ 20 mg. However, patients receiving corticosteroids must have been on a stable dosage regimen for a minimum of 4 weeks prior the study entry. Topical or inhaled corticosteroids are allowed.
5. Patients who have received immunization with attenuated live vaccines within one week of study entry (note: during study period these kinds of vaccines are also not allowed).

6. Patients who need treatment with inhibitors or potent inductors of CYP3A4

7. Patients who have any severe and/or uncontrolled medical conditions or other conditions that could affect their participation in the study such as:

- o Symptomatic congestive heart failure of New York heart Association Class III or IV
- o unstable angina pectoris, myocardial infarction within 6 months of start of study drug, serious uncontrolled cardiac arrhythmia or any other clinically significant cardiac disease
- o severely impaired lung function
- o uncontrolled diabetes as defined by fasting serum glucose  $>1.5 \times \text{ULN}$
- o active (acute or chronic) or uncontrolled severe infections
- o liver disease such as cirrhosis, chronic active hepatitis or chronic persistent hepatitis
- o a known history of HIV seropositivity.

8. Patients with an active, bleeding diathesis.

9. Female patients who are pregnant or breast feeding, or adults of reproductive potential who are not using effective birth control methods (e.g. total sexual abstinence\*, doble barrier methods like condom + spermicide, or condom + diaphragm with spermicide , intra-uterine device (IUD) and condom, diaphragm with spermicide, or vasectomize partner with azoospermia confirmed. Hormonal contraceptives are acceptable as a sole method of contraception.

Women able to conceive and using hormonal contraceptives have to be into the administration of a stable doses of the contraceptive at least 4 weeks before the first dose of drug study, during the whole study period and until 30 days after the study treatment will be retired. The women in fertile period must have a negative urine or serum pregnancy test within 7 days prior to administration of AZD2281.

The only women exempt of this requirement are the postmenopausal (define by not having a menstrual period for 12

	
consecutive months, from the corresponding group age, and without any other known or possible reason), the ones submitted to a chirurgic sterilization o can demonstrate sterility by other means (that is, chirurgic bilateral tubal ligation, and bilateral chirurgic hysterectomy or oophorectomy at least one month before the first dose of experimental drug administration.
 
*Total sexual abstinence will be acceptable only in the case that is in consonance with the way of life of the patient.
 
10. History of noncompliance to medical regimens.
 
11. Patients unwilling to or unable to comply with the protocol.

Study objectives:	
Primary Objective:
 
The primary objective of this study is to identify, the antitumoral biological efficacy, by measuring, biomarker changes associated to short exposure to AZD2281 as potential predictors of activity in Endometrial Carcinoma (EC) in human tumor samples.
 
This is an exploratory study with a biological primary endpoint.
 
Secondary Objectives
 
 
- To consider the tolerability to AZD2281 during the study and until 28 days after the last dose of AZD2281.
 
- To correlate changes induced by AZD2281 with the different type of endometrial carcinoma and other tumor biomarkers (NFkBp65 and p50, PARP, PARP-1, pHistone 2AX, pHistoneH3, VEGF (Vascular Endothelial Growth Factor), HIF(Hypoxia inducible factor)-1alpha).
 
- To estimate the potential predictive value of histological type: Endometrioid endometrial carcinoma (EEC) versus Non Endometrioid Endometrial Carcinoma (NEEC), and some biomarkers (immunostaining for PTEN (Phosphatase and tensin homolog), MLH-1 (mutL homolog 1), MSH-2 (mutS Homologue 2), MSH-6 (MutS homologue 6), PMS-2 (Postmeiotic Segregation Increased S. Cerevisiae. 2).
 

	
 
- To estimate the potential predictive role of microsatellite instability and PTEN loss in clinical tumor changes and PARP inhibition.
 
- To correlate clinical tumor changes with several targets of PARP inhibition.
 
- To further explore the use of Pharmacokinetic-dynamic modelling (PBMC modelling) as surrogate pharmacodynamic marker of AZD2281 activity in endometrial tumors.
 
- To quantify AZD2281 levels in human tissues after the oral administration of the drug
 
- To explore the correlation between intra-tumoral AZD2281 concentrations with plasma PK parameters and molecular alterations in EC after AZD2281 treatment.
 
- To compare intra-tumoral AZD2281 concentrations with those present in healthy tissues.
 
- To establish a kinetic-dynamic modelling, based on the status of the variables of time (t), concentration (C) in blood and in tissue, and molecular effect (E).
 
- To estimate the tolerability to AZD2281 throughout the study and up to 28 days after the last dose of AZD2281.
 

Type of study:	This is an open-label, non-randomized, non-controlled, multicenter phase 0 study that will enroll approximately 36 patients.
Therapy:	Eligible patients will receive 300mg of AZD2281 (two tablets of 150 mg of AZD2281) twice daily throughout 28 (+/- 5) days. Total daily dose will be 600 mg of AZD2281.
Evaluation Criteria:	
Primary Endpoint: The primary endpoint for this study is to assess the histological score of the cell cycle-related proteins cyclin D1, ki67 and active caspase 3, directly on endometrial tumor tissue after 28 (+/-5) days of therapy.
 
The histological score will be obtained by applying the following formula:

	
Hscore= 1x(%light staining) + 2x(%moderate staining) + 3x(%strong staining).
 
Secondary Endpoint-Safety
 
 
- To measure the correlation between PARP inhibitor effect and other changes in tumor-tissue:                     
 
o DNA repair: PARP, PARP-1, pHistone 2AX
 
o Mitosis: pHistone 2AX
 
o Angiogenesis (VEGF, HIF-1alpha)
 
o Apoptosis (NFkB p65, p50)
 
o Mutations and deletions
 
o Microsatellite instability
 
 
 
- AZD2281 blood levels on days 1, 7, 14, 21,28 of the therapy and day of surgery
 
- Drug tumoral tissue levels on day 28 of the treatment.
 
- Drug healthy tissue levels on day 28 of the treatment.
 
- To test the tolerability for all AZD2281-treated patients measured by CTCAE v.4.
 

Study follow-up:	
Inclusion period: 12 months.
 
Follow-up period: 28 days

### Appendix 1: Schedule of assessments and study procedures

Study Procedures	SCREENING Day (-14) -Day 0	BASELINE Day (-7) -Day 0	THERAPY PERIOD Day 1 – Day 28 (+/-5 days)	SURGERY or TC-biopsy Day 29	FOLLOW UP 28 days after last drug dose
Informed consent signed		X			
Anamnesis and Physical examination		X			
Concomitant medication record		X	D7-D14-D21-D28		
Functional status (WHO) and Vital signs		X	D7-D14-D21-D28		X
Safety assessment (CTCAE v 4.1)		X	D7-D14-D21-D28		X
Imaging assessment		X			
Standard laboratory procedures:					
Pregnancy test		X			
Hematology / Biochemistry values		X	D7-D14-D21-D28	X	X
Experimental laboratory (Sampling collection):					
Blood sample			D1 (before first dose), BS1 D1 (after first dose), BS2 D7, BS3, D14, BS4, D21, BS5 D28, BS6		D29 (before surgery), BS7

Study Procedures	SCREENING Day (-14) -Day 0	BASELINE Day (-7) -Day 0	THERAPY PERIOD Day 1 – Day 28 (+/-5 days)	SURGERY or TC-biopsy Day 29	FOLLOW UP 28 days after last drug dose
Formalin-fixed, paraffin-embedded (FFPE) tumor tissue	X MT1			X MT2	
Frozen tumor tissue	X (1)			X	

Tumor tissue samples will be obtained as follows:

- Biopsy: at least 1 paraffin-embedded biopsy will be obtained, prior to initiating therapy period. (1) It will be recommended to collect frozen tissue sample if possible.
- Surgical tumor section or biopsy samples will be obtained in the 24 hours following the last dose of therapy study. In case that surgical tumor sections are taken, 50% will be frozen and 50% paraffin embedded. In the case that biopsy samples are taken, at least 2 tumors will be obtained, 50% will be frozen and 50% paraffin embedded.

2 VERSION HISTORY

Version	Date	Status
Final version	11-Dec-2017	Final version

3 INTRODUCTION

3.1 Analysis summary and proposal

The main objective of the present study proposal is to assess the biological consequences of PARP inhibition in type I primary ECs, in patients who receive treatment with AZD2281 during the period of time between diagnosis and surgery. This is a phase 0 trial or "Exploratory Investigational New Drug" study, a type of trial that involves a limited number of patients under drug therapy and has the objective of anti-tumor biological efficacy. The purpose of the phase 0 studies is to assist in the go versus no-go decision-making process of a drug's fate earlier in the development process, using relevant human models instead of relying on sometimes inconsistent animal data, thus helping to confirm endpoints such as mechanism of action, pharmacology, bioavailability and pharmacodynamics.

In our proposal, the biologic effects will be assessed by comparing the expression of several targets of PARP inhibitors between the initial biopsy and tumor tissue at surgery, after PARP inhibition. The biomarkers that have been chosen are well known targets of PARP, which play a role in important cellular function: 1) Apoptosis (cleaved-caspase 3, NFkB), 2) DNA repair (Histone 2Ax phosphorylation), 3) cell proliferation (Ki-67, cyclin D1), 4) Mitosis (phosphohistone H3), 5) angiogenesis (VEGF, and HIF1alpha). Moreover, the possible predictive role of several pathological and molecular features (PTEN loss, Microsatellite instability (MSI), PARP expression) will be assessed. Therefore, changes in the expression of these markers would allow assessment of the effect of PARP inhibitors in these tumors.

4 OBJECTIVES AND ENDPOINTS

4.1 Study objectives

Primary Objective: The primary objective of this study is to identify anti-tumor biological efficacy by measuring, in human tumor samples, biomarker changes associated with short exposure to AZD2281 as potential predictors of activity in endometrial carcinoma (EC). This is an exploratory study with a biological primary endpoint.

Secondary objectives:

- To estimate the tolerability to AZD2281 throughout the study and up to 28 days after the last dose of AZD2281.
- To correlate changes induced by AZD2281 with the different type of endometrial carcinoma and other tumor biomarkers (NFkBp65 and p50, PARP, PARP-1, pHistone 2AX, pHistoneH3, VEGF (Vascular Endothelial Growth Factor), HIF(Hypoxia inducible factor)-1alpha).
- To estimate the predictive potential with regard to the following biomarkers (immunostaining for PTEN (phosphatase and tensin homolog), MLH-1 (mutL homolog 1), MSH-2 (mutS homolog 2), MSH-6 (mutS homolog 6), PMS-2 (Postmeiotic Segregation Increased S. Cerevisiae. 2).

- To estimate the potential predictive role of microsatellite instability (MSI) and PTEN loss in clinical tumor changes and PARP inhibition.
- To correlate clinical tumor changes with several targets of PARP inhibition.
- To further explore the use of Pharmacokinetic-dynamic modeling (PBMC modeling) as surrogate pharmacodynamic marker of AZD2281 activity in endometrial tumors.
- To establish a pharmacokinetic-dynamic modeling, based on the status of the variables of time (t), concentration (C) in blood, and molecular effect (E). PK-PD analysis will be performed based on the plasma concentration - PARP inhibition % in the tissue.

Secondary initial objectives that were dismissed:

- To quantify AZD2281 levels in human tissues after the oral administration of the drug.
- To explore the correlation between intratumoral AZD2281 concentrations with plasma PK parameters and molecular alterations in EC after AZD2281 treatment.
- To compare intratumoral AZD2281 concentrations with those present in healthy tissues.
- To establish a pharmacokinetic-pharmacodynamic modeling, based on the status of the variables of time (t) and concentration (C) in the tissue.

4.2 Variables

(ICH E9; 2.2.2)

4.2.1 Primary endpoint

Primary endpoint: The primary endpoint for this study is to assess the histological score of the cell cycle-related proteins cyclin D1, ki67 and active caspase 3, directly on endometrial tumor tissue after 28 (+/-5) days of treatment. The histological score will be obtained by applying the following formula:

Hscore= 1x(%light staining) + 2x(%moderate staining) + 3x(%strong staining).

4.2.2 Secondary endpoints:

Secondary endpoints:

- To measure the correlation between PARP inhibitor effect and other changes in tumor-tissue:

- DNA repair: PARP, PARP-1, pHistone 2AX
- Mitosis: pHistone 2AX
- Angiogenesis (VEGF, HIF-1alpha)
- Apoptosis (NFkB p65, p50)
- Mutations and deletions
- Microsatellite instability (MSI).

- AZD2281 blood levels on days 1, 7, 14, 21, the last day (28 +/- 5 days) of treatment and day of surgery.
- Drug levels in tumor tissue on the day of surgery.

- Drug levels in healthy tissue on the day of surgery.

4.2.3 Safety variables

- To test the tolerability for all AZD2281-treated patients measured as per Common Terminology Criteria for Adverse Events (CTCAE v.4).

5 STUDY DESIGN

5.1 Study design

(ICH E3;9.)

This is an open-label, non-randomized, uncontrolled, multicenter phase 0 study that will enroll approximately 36 patients. No efficacy objectives are included in this study. Randomization, blinding or control group are not required in this study design. The schedule of the assessments and the procedures performed in the patient is described in Tables 1 and 2.

Table 1. Study Schedule

[figure not shown]

Table 2. Study Procedure Schedule

Study procedures	SCREENING From Day (-14) to Day 0	START From Day (-7) to Day 0	TREATMENT PERIOD From Day 1 to Day 28 (+/- 5 days)	SURGERY or CT-biopsy Day 29	FOLLOW UP 28 days after the last dose of the drug
Signed informed consent		X			
Anamnesis and physical examination		X			
Concomitant medication record		X	D7-D14-D21-D28		
Performance status (WHO) and vital signs		X	D7-D14-D21-D28		X
Safety assessment (CTCAE v 4.1)		X	D7-D14-D21-D28		X
Imaging evaluations		X			
Standard laboratory procedures					
Pregnancy test		X			
Hematology/biochemistry values		X	D7-D14-D21-D28	X	X
Experimental laboratory (sample collection)					
Blood sample	BS1 BS2 BS3 BS4 BS5 BS6 BS7		D1 (Before the first dose) D1 (After the first dose) D7 D14 D21 D28		
Formalin-fixed, paraffin embedded (FFPE) tumor tissue	X			X	
Frozen tumor tissue	X ₍₁₎			X	
Tumor tissue samples will be obtained as follows:					

- Biopsy: At least one paraffin embedded biopsy will be obtained prior to initiating the therapy period.
 - (1) It will be recommended to collect the frozen tissue samples, if possible.
 - Surgical tumor sections or biopsy samples will be obtained in the 24 hours following the last dose of study treatment. In case that surgical tumor sections are taken, 50% will be frozen and 50% formalin-fixed and paraffin-embedded. In the case that biopsy samples are taken, at least 2 tumor samples will be obtained, 50% will be frozen and 50% paraffin embedded.

5.2 Study population

(ICH E3;9.3. ICH E9;2.2.1)

5.3 Target study population

This study will enroll patients with histologically confirmed type I primary endometrial carcinoma (EC).

5.3.1 Inclusion criteria

Patient eligibility should be reviewed and documented by an appropriate member of the investigator's study team before patients are enrolled in the study.

Patients are eligible for inclusion into the study only if they meet ALL of the following criteria:

1. Patients must have histologically confirmed type primary endometrial carcinoma (EC). Diagnosis biopsy must contain 3-12 mg of tumor cellularity/stroma (Tumor: 5-20 mm) and this will be checked in the central laboratory for this trial. If tumor cellularity/stroma is inadequate, one re-biopsy with adequate tumor cellularity/stroma will be mandatory before study entry.
2. Age \geq 18 years.
3. WHO performance status \leq 2.
4. Adequate bone marrow function as shown by: ANC \geq 1.5 \times 10⁹/L, Platelets \geq 100 \times 10⁹/L, Hb $>$ 10 g/dL
5. Adequate liver function as shown by:
 - o Serum bilirubin \leq 1.5 \times ULN
 - o INR $<$ 1.3 (or $<$ 3 on anticoagulants)
 - o ALT and AST \leq 2.5 \times ULN
6. Adequate renal function: Serum creatinine \leq 1.5 \times mg/dL.
7. Fasting serum cholesterol \leq 300 mg/dL or \leq 7.75 mmol/l and fasting triglycerides \leq 2.5 \times ULN.

NOTE: In case one or both of these thresholds are exceeded, the patient can only be enrolled after normalization values with appropriate lipid lowering medication.

8. Signed informed consent, including consent to tissue collection and blood samples as specified by the protocol.

5.3.2 Exclusion criteria

Patients will be excluded from the study if they meet ANY of the following criteria:

1. Subjects who have received prior anticancer therapies for the current endometrial cancer (including chemotherapy, radiotherapy, antibody-based therapy, hormone therapy or surgery).
2. Patients, who have had a major surgery or significant traumatic injury within 4 weeks of start of study drug, patients who have not recovered from the side effects of any major surgery (defined as requiring general anesthesia) or patients that may require major surgery during the course of the study.
3. Prior treatment with any investigational drug within the preceding 4 weeks.
4. Patients receiving chronic, systemic treatment with corticosteroids or another immunosuppressive agent, except corticosteroids with a daily dosage equivalent to prednisone \leq 20 mg. However, patients receiving corticosteroids must have been on a stable dosage regimen for a minimum of 4 weeks prior the study entry. Topical or inhaled corticosteroids are allowed.
5. Patients who have received immunization with attenuated live vaccines within one week of study entry (note: during study period these kinds of vaccines are also not allowed).
6. Patients who have any severe and/or uncontrolled medical conditions or other conditions that could affect their participation in the study such as:
 - o Symptomatic congestive heart failure of New York Heart Association Class III or IV.
 - o Unstable angina pectoris, myocardial infarction within 6 months of start of study drug, serious uncontrolled cardiac arrhythmia or any other clinically significant cardiac disease
 - o Severely impaired lung function
 - o Uncontrolled diabetes as defined by fasting serum glucose $>1.5 \times$ ULN.
 - o Active (acute or chronic) or uncontrolled severe infections
 - o Liver disease such as cirrhosis, chronic active hepatitis or chronic persistent hepatitis
 - o A known history of HIV seropositivity.
7. Patients with an active, bleeding diathesis.
8. Female patients who are pregnant or breast feeding, or adults of child-bearing potential who are not using effective birth control methods. If barrier contraceptives are being used, these must be continued throughout the trial by both sexes. Hormonal contraceptives are acceptable as a sole method of contraception. (Women of childbearing potential must have a negative urine or serum pregnancy test within 7 days prior to administration of AZD2281).
9. History of noncompliance to medical regimens.
10. Patients unwilling to or unable to comply with the protocol.

5.4 Sample size calculation

(ICH E3; 9.7.2. ICH E9; 3.5)

The primary objective is to identify, in human tumor samples, biomarker changes associated with short exposure to AZD2281 as potential predictors of activity in Endometrial Carcinoma (EC). The primary endpoint is the difference between pre and post treatment immunostaining of cyclin D1, Ki67 and active caspase 3 on endometrial tumor tissue, after four weeks of treatment. Therefore, the primary analysis will be based on comparing pre and post treatment immunostaining on target biomarkers. The histological

score will be obtained by applying the following formula: $Hscore = 1x(\%light staining) + 2x(\%moderate staining) + 3x(\%strong staining)$. Although a preliminary power analysis has been performed, in agreement with the exploratory nature of phase 0 studies, the sample size has been limited to 36 patients (It is expected that each participating site includes an average of about 6-10 patients) for clinical and practical considerations, rather than statistical ones (Kummar et al 2009).

Analysis will be performed in accordance with a statistical evaluation scheme specifically developed for Phase 0 trials (Rubinstein et al 2010). In the analysis we will define response at the patient level (patients with significant inhibition of biomarkers), before analyzing the number of responding patients in the study sample.

Definition of response at the patient level:

Significant inhibition of biomarker activity is defined as the reduction in biomarker levels after four weeks treatment exposure (compared to baseline) that should satisfy two criteria: reduction is at least 50 % (biological), and reduction is sufficient when compared to the variation among the baseline values, to yield 95 % statistical confidence that it is not due to chance variations.

Variability will be measured on log-transformed values. The standard deviation (SD) will be the square root of baseline inter-patient variance. Pre- and post-treatment difference of log PIK1 values will be compared to the threshold of 1.6448 SD (normal distribution is used because number of samples is higher than 30), to establish statistically significant reduction at the one-sided 0.05 level.

Definition of a significant effect at study sample:

Significant inhibition of biomarker activity will be declared if 5 of 36 patients have significant inhibition at patient level. Based on these assumptions, there is a 95% power to detect a true 35% rate of significant inhibition with an overall alpha error below 10%. As we consider three biomarkers in the primary analysis (cyclin D1, Ki67 and active caspase 3), the type I error was divided into 3,3% (<5%) for each analysis. Power and type I error has been derived from the binomial distribution (Rubinstein et al 2010), according to (A'Hern 2001).

Study dropouts

We assume the loss of patients between recruitment and end of study. Study dropouts will be analyzed as patients not displaying significant inhibition of the biomarker activity.

5.5 Randomization and blinding.

(ICH E3; 9.4.3, 9.4.6. ICH E9; 2.3.1, 2.3.2)

The randomization or blinding was not planned in this study.

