7.2 Populations for analysis

(ICH E3; 9.7.1, 11.4.2.5. ICH E9; 5.2)

Full analysis set

This set will include all the patients who have received the treatment. This set will also be the safety analysis set.

Per protocol set

This set will include all the patients of the full analysis set that do not have major protocol violations that may affect the assessment of treatment in the primary variable (e.g., non-evaluable patients for

biomarkers). The definition of these deviations is described in section 9.1. For the analysis of secondary variables, the number of evaluable patients for a certain biomarker analysis set will be considered.

Sensitivity analysis

The primary biomarker analysis (significant inhibition of cyclin D1, Ki67 and active caspase-3) and the secondary analyses will be performed in the full analysis set and the per protocol population.

The safety analyses will be performed in the full analysis set.

PKD population

We propose to analyze and model pharmacokinetics (PK), pharmacokinetics-pharmacodynamic (PBMC) and AZD2281 concentration, considering all patients with a complete treatment concentration-time profile.

Analyses will not be repeated between different analysis populations if they only differ by 10% patients. The largest analysis population will be used for the analyses.

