7.6 Missing data imputation

(ICH E3; 9.7.1, 11.4.2.2. ICH E9; 5.3. EMA Guideline on Missing Data in Confirmatory Clinical Trials)

Patients without quantitative biomarker values at the baseline visit will be assigned the mean of the patients at that visit. Patients without quantitative values at the follow-up visits will be assigned the same value as in the baseline visit. This imputation is intended to be conservative and go against the study objective (to detect a significant evolution between pre- and post-treatment biomarker values). In the case of qualitative variables, the lack of mutation or the characteristic analyzed will be assumed.

The different study populations where the different analyses will be performed will help to assess the imputation on the results. The analyses are only considered positive if the result is equivalent in all the analysis populations used.

7.7 Analysis of the specific effects of each site.

(ICH E3; 9.7.1, 11.4.2.4. ICH E9; 3.2)

The number of patients enrolled in each site will be described. Considering the small sample size, no analyses are expected to adjust the results by the site effect.

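### SAP 5.4 counts only a fall as response and applies this to active caspase 3, which the SAP lists under apoptosis, without stating or justifying that direction

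*SAP*

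**What the plan says.** SAP 4.1 gives the aim: "The primary objective of this study is to identify anti-tumor biological efficacy by measuring" biomarker changes in tumor samples. SAP 4.2.1 makes the primary endpoint "the histological score of the cell cycle-related proteins cyclin D1, ki67 and active caspase 3", with no direction for any of them.

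SAP 5.4 sets the decision rule at two levels.

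- Patient level: "Significant inhibition of biomarker activity is defined as the reduction in biomarker levels after four weeks treatment exposure (compared to baseline", subject to two conditions. The fall must be at least 50%, and it must exceed 1.6448 baseline SDs on the log scale (one-sided 0.05).
- Study level: "Significant inhibition of biomarker activity will be declared if 5 of 36 patients have significant inhibition at patient level". The overall alpha of 10% is split into 3.3% for each of cyclin D1, Ki67 and active caspase 3.

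SAP 7.2 repeats the wording for all three markers: "The primary biomarker analysis (significant inhibition of cyclin D1, Ki67 and active caspase-3". SAP 7.8 does the same. Neither makes an exception for caspase 3. The sentence in 5.4 that holds the SD cut names log PIK1, which is not a primary marker. Applying the cut to the three primary markers is the reading that the rest of 5.4, 7.2 and 7.8 require.

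SAP 3.1 sorts the markers by function. Ki-67 and cyclin D1 come under cell proliferation, but caspase 3 comes under "1) Apoptosis (cleaved-caspase 3, NFkB". I read cleaved and active caspase 3 as the same marker.

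**The concern.** A fall in Ki67 or cyclin D1 fits a drug that slows proliferation. An apoptosis marker need not move the same way: if the drug kills tumor cells, one would expect active caspase 3 to rise. The plan tests all three in the downward direction and gives no reason for doing so with caspase 3.

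For that marker, then, the rule that declares the primary result cannot register a rise of any size, and it can return a positive result on a fall. SAP 3.1 says that phase 0 studies inform go or no-go decisions, and 6.1 plans to present interim primary results publicly. If direction is settled only after the post-treatment scores are seen, the choice is driven by the data.

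**Working it through.** **Inputs from SAP 5.4:** 36 patients; at least 5 responders; cut of 1.6448 SD; at least a 50% fall; null patient-level rate 0.05 (from the one-sided 0.05 criterion).

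**The plan's own figures.** P(Bin(36, 0.05) ≥ 5) = 0.0324, and 3 × 0.0324 = 0.0971. Both agree with the stated 3.3% and 10%. At a true rate of 35% the exact power is 0.999, not the stated 95%; that is a separate matter and nothing here depends on it.

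**Model (assumptions, not in the documents).** Log differences are normal, the pre and post SDs both equal s, the correlation is ρ, the mean shift is δ baseline SDs, and the H-score has no ceiling.

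- Cut: T = max(1.6448 s, ln 2). The two criteria cross at s = 0.6931/1.6448 = 0.421, so above 0.42 the SD cut binds.
- SD of the difference: s√(2(1 − ρ)), which equals s at ρ = 0.5.
- At ρ = 0.5 and s above 0.42: P(fall counts) = Φ(−1.6448 − δ); P(rise counts under a mirrored rule) = 1 − Φ(1.6448 − δ).
- Declaration: P(Bin(36, p) ≥ 5), one look, all 36 evaluable.

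| True shift in caspase 3 | Written rule: p per patient | Written rule: declared | Upward rule: p per patient | Upward rule: declared |
|---|---|---|---|---|
| none | 0.0500 | 0.032 | 0.0500 | 0.032 |
| rise 0.5 SD | 0.0160 | 0.0003 | 0.1261 | 0.483 |
| rise 1 SD | 0.0041 | 4 × 10⁻⁷ | 0.2595 | 0.974 |
| fall 1 SD | 0.2595 | 0.974 | 0.0041 | 4 × 10⁻⁷ |

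**Dropouts.** With 3, 6 or 9 of the 36 counted as non-responders, a 1 SD fall is still declared by the written rule with probability 0.954, 0.920 or 0.867.

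**Interim condition in 7.8.** I read it as an exact binomial p below 0.033 against 5%, at an assumed interim size of 12, 18, 24 or 30. This needs 3, 4, 4 or 5 responders at the interim. The joint probability of passing it and reaching 5 of 36 after a 1 SD fall is 0.636, 0.725, 0.900 or 0.920 (no dropouts).

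**Other correlations.** At ρ = 0, 0.25 and 0.75 a 1 SD rise is declared by the written rule with probability 0.5%, 0.02% and about 0, against 99.7%, 99.3% and 80.5% for the upward rule. The null rate is no longer 5% there (12.2% at ρ = 0, 1% at ρ = 0.75), so these figures show direction only and are not power claims.

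**Smaller SD.** Below s = 0.42 the ln 2 criterion binds. At ρ = 0.5, power for a 1 SD shift in the counted direction is 94% at s = 0.40, 72% at 0.35 and 25% at 0.30, the same for either rule.

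**Counting both directions.** The null rate becomes 0.05 + 0.05 = 0.10, and P(Bin(36, 0.10) ≥ 5) = 0.289. The three-marker sum is 0.289 + 2 × 0.0324 = 0.354.

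**H-score ceiling.** The formula cannot exceed 3 × 100 = 300, so a patient with baseline above 150 cannot double. I capped scores at 300 in the same model (ρ = 0.5, log SD 0.45 to 0.60 before capping, cut computed from the capped baseline scores). Power of an upward rule with a doubling criterion for a 1 SD rise is then about 97% at an assumed baseline median of 50, 85–91% at 150 and 58–75% at 200. Power of the written rule for a 1 SD fall stays at 97–99%. Dropping the doubling would not remove all of this loss, because above log SD 0.42 the SD cut already asks for more than a doubling (exp(1.6448 × 0.42) = 2.0).

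**The case against.** The strongest reply is that no passage calls a caspase 3 rise favourable. SAP 3.1 names functions, not directions, and puts NFkB under the same label; 4.2.1 calls all three markers cell cycle-related; and 5.1 says the study has no efficacy objectives. If caspase 3 fell, a declaration of inhibition would be literally true. This stands as a limit: the favourable direction is an inference. It does not rescue the rule. The 5.1 statement conflicts with the primary objective in 4.1, and the label in 4.2.1 gives no reason to test an apoptosis marker downward only.

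A reader might infer that the study would miss a rise altogether. It would not. The Wilcoxon comparison (7.1), the pre/post differences in 7.3 and Figure 2, which names caspase 3, could all show it. None of them feeds the 5-of-36 count.

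A reader might also infer that 5 falls would by themselves secure a positive claim. SAP 7.6 adds that "The analyses are only considered positive if the result is equivalent in all the analysis populations used", and 7.8 requires p below 3.3% at both interim and final analyses. Dropouts also count against a positive result: "Study dropouts will be analyzed as patients not displaying significant inhibition of the biomarker activity". These conditions make a declaration harder, but they do not change its direction.

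Extending the fault to Table 3 or 7.5 goes too far. Table 3's title names no marker. SAP 7.5 relies on a protocol page outside the supplied synopsis, and its list of correlated markers omits caspase 3.

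**Conclusion.** Wrong as written, limited to one of the three primary markers. That the rule counts only falls and covers caspase 3 follows from the SAP text and needs no model. That a rise is the favourable direction is inferred. What the documents establish is that the direction tested is neither stated as expected for this marker nor justified. They do not support saying that the whole primary analysis is invalid: the cyclin D1 and Ki67 tests stand.

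The size (below 0.0001 against 97% for a 1 SD rise, and 97% for a 1 SD fall) is an illustration that rests on normal log differences, equal SDs, correlation 0.5, log SD above 0.42, 36 evaluable patients, one look and no ceiling. The asymmetry persists at the other correlations tried; the exact figures do not.

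**What to change.** Before post-treatment caspase 3 scores are analysed, state the direction by marker in SAP 5.4, 7.2 and 7.8, and name the primary markers where 5.4 now says log PIK1. Keep reduction for cyclin D1 and Ki67. For active caspase 3, choose one of the following:

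- a one-sided increase rule (log post minus log pre above +1.6448 SD), keeping 5 of 36 and the alpha split, with an upward biological criterion that the sponsor chooses and justifies against the observed range of baseline H-scores; or
- the present rule, with a stated reason why a fall is the expected effect.

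Do not count both directions at the same cut, since per-marker alpha would be 28.9%. Make Table 3 and 7.5 consistent with the choice.

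The cost is SAP wording and a direction flag in the code. No patients, samples or alpha are needed: in the model above, the upward SD cut has the same null rate as the downward one. There are two downsides to the increase rule. A caspase 3 fall would be described but could no longer be declared. The ceiling of 300 would also cost power if baseline scores are high, so a doubling should not be adopted as an automatic mirror of the 50% fall.
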